8. ANALYSES AND SUMMARIES

a. DESCRIPTIVE STATISTICS

For continuous and pseudo-continuous variables, the number of observations, number of missing values, mean, standard deviation, median, twenty-fifth percentile, and seventy-fifth percentile will be given. For yes/no, categorical, and/or ordinal variables a simple count and percent or frequency will be given. Other statistics may be considered if necessary.

b. DEMOGRAPHIC AND BASELINE CHARACTERISTICS

Demographic and baseline characteristic data will include age (based on date of informed consent), sex, race, ethnicity, height, weight, and body mass index (BMI). All demographic and baseline characteristic data will be summarized. An analysis of variance [ANOVA] will be used to assess homogeneity regarding demographic characteristics between treatment groups.

c. MEDICAL HISTORY

Medical history is collected at screening and will be summarized by treatment group.

d. EFFICACY ANALYSES

PK is a surrogate for efficacy, since a titer of ≥ 0.5 IU/mL is well-established as protective against the rabies virus. RVNA titers will be listed for each subject, and summary statistics for each timepoint presented by treatment group.

e. PRIMARY EFFICACY ANALYSIS

The primary efficacy analysis will be based on the primary PK population.

The primary hypothesis is that the proportion of subjects receiving BPL HRIG + active vaccine with an anti-rabies antibody of ≥ 0.5 IU/mL will not be less than the corresponding proportion for subjects receiving comparator HRIG + active vaccine, by more than 0.1 at Visit 6. The Farrington and Manning test statistic will be used to assess the statistical comparison of the proportions at a one-sided significance level of [REDACTED]. It will be concluded that the BPL HRIG is non-inferior to the comparator HRIG if the lower limit of an exact binomial 95% confidence interval is greater than the *a priori* set [REDACTED] non-inferiority margin.

HYPOTHESIS

The null hypothesis is $p-p_0 \leq -0.1$;

The alternative hypothesis is $p-p_0 > -0.1$,

where p is the proportion of subjects with RVNA titer of ≥ 0.5 IU/mL at Visit 6 in subjects receiving BPL HRIG + vaccine and p_0 is the proportion receiving comparator HRIG + vaccine

We reject the null hypothesis at the one-sided [REDACTED] significance level, and conclude that $p-p_0 > -0.1$, if the lower bound of an exact 95% binomial confidence interval exceeds -0.1.

DERIVATION OF PRIMARY ENDPOINT

[REDACTED] will be performing the RFFIT test and providing the results for data analysis. Subject serum will be tested in duplicates. If either individual test in duplicated set 1 fails QC, a second duplicate set of RFFIT tests will be run. The arithmetic mean value of the appropriate duplicate set, (set 1 if QC passed, set 2 if QC failed), will be used for the final reported rabies antibody titer [IU] for primary endpoint derivation. If the final arithmetic mean value is ≥ 0.5 IU/mL that subject-specific time point will be coded as 1 (success); otherwise if the final arithmetic mean value is < 0.5 IU/ml the time point will be coded as 0 (failure). If both duplicate sets fail the QC test,

the subject data is deemed non-evaluable. The proportion of subjects with RVNA titer ≥ 0.5 IU/mL is calculated as follows:

$$\frac{\sum(\text{successes}, 1)}{\sum(\text{all evaluable subject } i, n)}$$

Sensitivity analyses will be performed to assess impact of missing data, see section 8j.

f. SECONDARY EFFICACY ANALYSES

Secondary efficacy analyses 2 and 5 will be based on the secondary PK population. Secondary efficacy analyses 1, 3, and 4 will be based on the primary PK population, since timepoints post-Visit 6 are not included in these analyses.

The second secondary analyses will be performed using an appropriate mixed model repeated measures [MMRM] analysis to assess for differences of the slope and the change in GMT of the titers at the days described below. The correlation structure involves multiple pieces, including measurement errors, random variation, and inter-individual variability. For the longitudinal data analysis, an unstructured correlation matrix for within-subject error will be assumed. Other correlation structures, including compound symmetry, will be examined as needed. The validity of this model will be assessed via standard modeling diagnostics and goodness-of-fit measures. Comparisons of geometric mean titers [GMTs] between the treatment group at each timepoint and across all timepoints will be reported. The final output will include one row indicating the mean change [95% confidence intervals] in titer across all PK assessments from Visit 2 [baseline] through Visit 7 by treatment group and one row for every specific timepoint thereafter. Additionally, the difference in the means [or the ratio of the GMT] between treatment groups, the corresponding 95% confidence intervals, associated chi-square test statistic, and p-value will be reported. A p-value of <0.05 will signal a statistically significant difference in titers. See table below for example output:

Parameter	Treatment Group Ns			Mean Change From Baseline (95% Confidence Intervals)		BPL HRIG + Vaccine versus Comparator HRIG + Vaccine		
	N _{BPL}	N _{CP}	N _T	BPL HRIG + Vaccine	Comparator HRIG + Vaccine	Difference in Means (95% CI)	Chi-Square	P-Value
Through Day 28	x	x	x	x.xx (x.xx, x.xx)	x.xx (x.xx, x.xx)	x.xx (x.xx, x.xx)	x.xx	0.xxx
Day 3	x	x	x	x.xx (x.xx, x.xx)	x.xx (x.xx, x.xx)	x.xx (x.xx, x.xx)	x.xx	0.xxx
Day 5	x	x	x	x.xx (x.xx, x.xx)	x.xx (x.xx, x.xx)	x.xx (x.xx, x.xx)	x.xx	0.xxx
Day 7	x	x	x	x.xx (x.xx, x.xx)	x.xx (x.xx, x.xx)	x.xx (x.xx, x.xx)	x.xx	0.xxx
Day 14	x	x	x	x.xx (x.xx, x.xx)	x.xx (x.xx, x.xx)	x.xx (x.xx, x.xx)	x.xx	0.xxx
Day 28	x	x	x	x.xx (x.xx, x.xx)	x.xx (x.xx, x.xx)	x.xx (x.xx, x.xx)	x.xx	0.xxx

1. a one-sided t-test will be used to assess non-inferiority of the mean of the AUC_{0-7d} of the BPL HRIG + vaccine group to the comparator HRIG + vaccine group. The pre-specified non-inferiority margin is 20%. It will be concluded the mean AUC_{0-7d} in the BPL HRIG + vaccine group is non-inferior to that in the comparator group if the lower limit of the 95% confidence interval for the mean AUC_{0-7d} is greater than -20% of comparator mean AUC_{0-7d}. Log-transformation of the AUC_{0-7d} data will be performed as necessary during statistical testing to meet assumptions for normality.

The null hypothesis is $(\mu_T - \mu_C) / \mu_T \leq -0.2$;

The alternative hypothesis is $(\mu_T - \mu_C) / \mu_T > -0.2$;

Where μ_T =the geometric mean of the AUC_{0-7d} in the BPL HRIG + vaccine group,

μ_C =the geometric mean of the AUC_{0-7d} in the comparator HRIG + vaccine group.

2. The geometric mean titers (GMTs) for RVNA titer up to peak serum level after administration of BPL HRIG and vaccine versus comparator HRIG and vaccine. Due to the observed change in relationship between time and titer level, only PK timepoints up to peak serum level will be included in this analysis.

A generalized estimating equation [GEE] for a repeated measures analysis will be used to assess the difference in proportions between the treatment groups for the third and fourth secondary efficacy analyses. Standard model building methods, diagnostics, and goodness-of-fit measures will be performed as appropriate. Proportions of subjects reaching set anti-rabies antibody titer will be compared at each timepoint as well as throughout all timepoints.

3. The proportion of subjects reaching anti-rabies antibody titer of ≥ 0.5 IU/mL at Visits 3-6 after administration of BPL HRIG and vaccine versus comparator HRIG and vaccine.
4. The proportion of subjects reaching anti-rabies antibody titer of \geq the lower limit of quantitation of the assay at Visit 3-6 after administration of BPL HRIG and vaccine versus comparator HRIG and vaccine. This titer threshold corresponds to the lower limit of quantitation of the assay.

The GEE analysis will include timepoints through Visit 6 for endpoints 3 and 4, at which point all or nearly all subjects are expected to have reached the stated thresholds. There is no clinical benefit of including subsequent timepoints in this analysis.

5. The geometric mean titers (GMTs) for anti-rabies antibody titer at Visit 6-9 will be compared between treatment groups. Descriptive statistics and visual inspections will be reported as appropriate. No formal hypotheses testing will be performed.

g. EXPLORATORY PK ANALYSES

The following PK parameters for anti-rabies antibody concentrations will be summarized for both treatment groups:

- C_{\max} [IU/mL]
- T_{\max} [day]
- area under the concentration vs time curve to the last measurable concentration (AUC_{0-t}) [day*IU/mL]
- apparent terminal rate constant (λ_z) [day⁻¹]
- AUC_{0-7d} [day*IU/mL]
- area under the concentration vs time curve to infinity ($AUC_{0-\infty}$), if appropriate

- $C_{\max}/AUC_{0-\infty}$ [or C_{\max}/AUC_{0-t} if $AUC_{0-\infty}$ cannot be estimated]
- half-life ($t_{1/2}$), if appropriate

Non-compartmental PK methods will be utilized to calculate the subject level PK parameters. C_{\max} , AUC_{0-t} , AUC_{0-7d} , $AUC_{0-\infty}$, apparent terminal rate constant (λ_z), and $t_{1/2}$ will be dose normalized by dividing the raw PK parameters by the actual dose the subject received. A t-test will compare the PK and dose-normalized PK parameters between treatment groups. Log-transformations will be performed as necessary during statistical analysis when appropriate.

h. ADVERSE EVENT REPORTING

Adverse events (AEs) will be reported by the MedDRA system organ class and preferred term. Only treatment emergent AEs (i.e. beginning after dosing with BPL HRIG / vaccine or comparator HRIG / vaccine) will be included in the summary tables. All AEs will be included in the data listings.

Treatment-related AEs will be defined as events recorded as having a possible, probable or very likely/certain causality to treatment. AEs leading to withdrawal will be defined as events where the subject's participation in the study was discontinued as a result of the AE.

AEs will be summarized descriptively for all subjects and by treatment group. The denominator used for the calculation of percentages will be the number of subjects in the safety population per treatment group. For all AE summaries described below, counting will be performed by subject and event. For counts by subject, subjects experiencing the same event more than once will have that event counted only once within each system organ class and once within each preferred term.

The following summaries of treatment-emergent AEs will be provided:

SUMMARY OF AEs

- The number and percentage of subjects reporting AEs, serious AEs, study medication-related AEs, AEs leading to withdrawal and AEs leading to death.
- The number of AEs, serious AEs, study medication-related AEs, AEs leading to withdrawal and AEs leading to death.

SUMMARY OF AEs BY SEVERITY OF EVENT

The number and percentage of subjects reporting AEs, and study medication-related AEs, will be summarized by the system organ class and by the preferred term. The severity of event will be recorded once per subject for each term as the maximum severity experienced by each subject (i.e. where the order of most severe to least severe is given by: severe, moderate and then mild).

SUMMARY OF AEs BY CAUSALITY

The number and percentage of subjects reporting AEs will be summarized by the system organ class and by the preferred term. The causality will be recorded once per subject for each term giving the most likely relationship to study medication (i.e. in the order: very likely/certain, probable, possible, unlikely and then unrelated).

i. SENSITIVITY ANALYSES

Sensitivity analyses will be performed to assess the impact on the primary PK analysis of non-compliers within the ITT population, missing primary endpoints, and timing of vaccine dosing.

POTENTIAL INTERACTION

Before treatment unblinding, timing of vaccine dosing and PK sampling, if not performed on the designated day, will be assessed as potential effect modifiers on the association between RVNA levels and treatment group in the primary and secondary PK analysis. A chi-square or fisher's exact test, as appropriate, will be used to measure the association between the dichotomous indicator of receiving dose/PK sampling on the intended day

[yes/no] and target level of RVNA titer reached [yes/no]. If the association is significant at the 0.05 level, a subgroup analysis including only subjects who were dosed/sampled on the target day will be reported in addition to the full analysis.

NON-COMPLIERS AND MISSING DATA

Non-compliers will be defined as subjects who meet one of the following:

- subjects who did not receive the full dose of BPL HRIG/comparator HRIG [not eligible for primary PK population];
- all 3 doses of active rabies vaccine at the time specified [not eligible for primary PK population];
- randomized without meeting all eligibility criteria [REDACTED];
- subjects with any major protocol deviations reported [REDACTED].

Specifically, the following two analyses will be performed to assess impact on primary PK analysis:

- The primary PK analysis will be repeated assuming that non-compliant subjects did not attain an RVNA titer of ≥ 0.5 IU/mL at Visit 6. [worst case scenario]
- The primary PK analysis will be repeated assuming that non-compliant subjects successfully attain an RVNA titer of ≥ 0.5 IU/mL at Visit 6. [best case scenario]

j. SUBGROUP ANALYSES

Subgroup analyses will be performed as appropriate, due to either imbalance randomization in baseline subject demographics and/or clinical relevance to primary and secondary PK analyses and safety analysis. Factors including, but not limited to, age, race, BMI, and sex will be considered. Subgroups will be defined based on population median.

K. MISSING VALUES

No missing value imputation methods will be applied, e.g. the analyses are based on a valid case basis.

I. INJECTION SITE OBSERVATIONS

Injection site observations data will be summarized as appropriate.

SUMMARY BY PRODUCT

The number and percentage of subjects reporting injection site reactions will be summarized by preferred term and product (HRIG or vaccine).

SUMMARY BY NUMBER OF INJECTIONS

The number and percentage of subjects reporting injection site reactions will be summarized by preferred term, product (HRIG or vaccine) and number of injections.

M. VIRAL SEROLOGY VARIABLES

Viral serology variables will be summarized. Shift tables for virology will present the number of subjects with positive and negative results and those for whom the results change during the study.

N. HEMATOLOGY, SERUM BIOCHEMISTRY, URINALYSIS

Hematology, serum biochemistry and urinalysis variables will be summarized, including changes from baseline. Shift tables for hematology and biochemistry variables will be provided for the number and percentage of subjects with values below, within and above the reference range.

O. MARKERS OF HEMOLYSIS

Markers of hemolysis will be summarized, including changes from baseline.

p. VITAL SIGNS AND BODY TEMPERATURE

Sitting diastolic and systolic blood pressure, pulse rate, body temperature and respiration rate will be summarized, including changes from baseline (i.e. pre-dose on Visit 2 for body temperature, Screening for all other parameters). In addition, the number of subjects with “substantial” increases or decreases from baseline in blood pressure (>20 mmHg) and pulse (>15 b.p.m.) will be summarized.

q. PHYSICAL EXAMINATION

Physical Examination and ECG findings will be summarized. The shift from Screening to Visit 8 and Screening to the End-Study Assessment will be summarized. Body weight data will be fully listed.

r. OTHER SAFETY PARAMETERS

Pregnancy test results will be listed.

s. INTERIM ANALYSIS

No interim analysis is planned.

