10.5.1. Primary PK Analysis

The primary efficacy analysis will be based on the primary PK population.

The primary hypothesis is that the proportion of subjects receiving BPL HRIG + active vaccine with an anti-rabies titer of ≥ 0.5 IU/mL will not be less than the corresponding proportion for subjects receiving comparator HRIG + active vaccine, by more than 0.1 at Visit 6. The Farrington and Manning test statistic will be used to assess the statistical comparison at a one-sided significance level of 0.025. It will be concluded that the BPL HRIG is non-inferior to the comparator HRIG if the lower limit of an exact binomial 95% confidence interval calculated from the Farrington-Manning score test is greater than the *a priori* set -10% non-inferiority margin.

An additional analysis will be performed to assess the impact of dosing/PK sampling not being performed on the designated day. See Section 10.7.2.

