10.9. Determination of Sample Size

Statistical calculations indicate a minimum of 73 subjects per group is necessary. To allow for subject withdrawals or unevaluable data, approximately 81 subjects will be enrolled per group.

This study is powered based on a one-sided test with an overall study α of 0.05. A total of 162 subjects will be randomized to achieve 85% power with a one-sided significance level of 0.025.

This computation accounts for an expected 10% dropout rate resulting in 146 evaluable subjects. The following table outlines the underlying assumptions:

Table 7: The underlying assumptions

	Day 14 \geq 0.5 IU/mL
Non-inferiority margin	10%
Difference	0%
% success	98%

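### Baseline is tested by ANOVA and imbalance is answered only with median-split subgroups, while the AUC0-7d and GMT analyses name no baseline covariate: valid, but precision and protection against chance imbalance are given up

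*SAP*

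**What the plan says.** **Baseline.** SAP 8.b lists age, sex, race, ethnicity, height, weight and BMI, to be summarized. It adds: "An analysis of variance [ANOVA] will be used to assess homogeneity regarding demographic characteristics between treatment groups". It sets no significance level and names no other test for categorical variables.

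**Response to imbalance.** SAP 8.j: "Subgroup analyses will be performed as appropriate, due to either imbalance randomization in baseline subject demographics and/or clinical relevance" to the PK and safety analyses. The factors to be considered include age, race, BMI and sex; protocol 10.8 has the same rule without BMI. Both documents add: "Subgroups will be defined based on population median". The sensitivity analyses (protocol 10.7, SAP 8.i) deal with non-compliance, missing endpoints and visit timing, not baseline imbalance. Neither document describes stratified randomization.

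**Models.** In SAP 8.f, "a one-sided t-test will be used to assess non-inferiority of the mean of the" AUC0-7d, with a 20% margin and no covariates. The mixed model for GMTs is specified by its correlation structure and names no covariate. The GEE for the titer proportions allows standard model building, again with no covariate named.

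**Primary test and sample size.** The primary analysis asks whether the BPL HRIG proportion is lower "by more than 0.1 at Visit 6", by the Farrington-Manning score test. Protocol 10.9 states: "Statistical calculations indicate a minimum of 73 subjects per group is necessary".

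**The concern.** Three things do not fit together.

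1. In a properly randomized trial, a test of baseline homogeneity asks whether a difference arose by chance when it is already known that it did. The p-value says nothing about whether a covariate matters for titer. For race, which has several unordered levels, ANOVA is also the wrong tool.
2. The named response does not address the problem. Results within subgroups leave the overall between-arm difference where it was; adjustment for the covariate is what removes the part due to imbalance. The median rule also cannot be carried out for two of the factors listed, sex and race.
3. The analyses that could benefit from adjustment do not use it. Protocol 2.9 gives the purpose of AUC0-7d as comparing the HRIGs before the vaccine response appears. It is the only secondary endpoint with a non-inferiority margin, and neither document gives a power calculation for it.

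At stake are the width of the AUC0-7d and GMT confidence intervals, and the credibility of those comparisons if the arms happen to differ in age, sex or body size.

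**Working it through.** **1. The plan's own figure.** Inputs from protocol 10.9: 98% success in both arms, margin 0.10, one-sided 0.025, power 85%. Farrington-Manning formula: n = [(z0.975·s0 + z0.85·s1)/0.10]².
- Restricted maximum-likelihood proportions under a difference of −0.10 are 0.8895 and 0.9895, so s0 = √(0.8895×0.1105 + 0.9895×0.0105) = 0.3296.
- s1 = √(2×0.98×0.02) = 0.1980.
- n = [(1.960×0.3296 + 1.036×0.1980)/0.10]² = 72.4, rounded up to 73. This matches the protocol.
- 162 × 0.9 = 145.8, the stated 146 evaluable.

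None of this depends on covariates, and the fix leaves it unchanged.

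**2. Baseline tests.** If each of k tests used 0.05 (a level the SAP does not state) and the tests were independent, the chance of at least one flag under correct randomization would be 1 − 0.95^k: 30.2% for k = 7 and 18.5% for k = 4. Height, weight and BMI are correlated, so 30% is too high for the seven listed.

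**3. ANOVA on a two-level variable.** For an illustrative split of 48/81 against 36/81, ANOVA gives p = 0.0597 and the uncorrected chi-square p = 0.0592. The misfit is therefore negligible for sex and matters for multi-level race.

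**4. Precision from adjustment.** R² is the share of log-AUC or log-titer variance explained by age, sex and BMI. It is in neither document; the range 0 to 0.30 is assumed. The standard error is multiplied by √(1 − R²):

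| R² | 0.02 | 0.05 | 0.10 | 0.20 | 0.30 |
|---|---|---|---|---|---|
| SE factor | 0.990 | 0.975 | 0.949 | 0.894 | 0.837 |

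**5. AUC0-7d power.** 73 per arm, true ratio 1, one-sided 0.025, log scale. SD = √ln(1 + CV²), SE = SD·√[(1 − R²)·2/73], power = Φ(−ln(bound)/SE − 1.96). CV is also an assumption.

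Example with CV 50% and bound 0.80: SD = √ln 1.25 = 0.472; SE = 0.0782 at R² = 0; power = Φ(0.2231/0.0782 − 1.96) = 81%.

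| CV | R² = 0 | 0.10 | 0.20 | 0.30 |
|---|---|---|---|---|
| 40% | 93.8% | 95.8% | 97.5% | 98.7% |
| 50% | 81.4% | 85.3% | 89.1% | 92.7% |
| 60% | 68.1% | 72.7% | 77.6% | 82.8% |

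At CV 50% and R² of 0.02 and 0.05, power is 82.2% and 83.3%, a gain of about 1 to 2 points. At CV 30% it is already 99.6% without covariates.

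**6. Which bound.** The confidence-interval rule in SAP 8.f measures the 20% against the comparator mean, a ratio bound of 0.80. The null written below it divides by the test mean: 1 − μC/μT ≤ −0.2 gives μT/μC ≤ 1/1.2 = 0.833. Under that bound, power at CV 50% is 64.5% at R² = 0, 69% at 0.10 and 80% at 0.30.

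**7. A realized imbalance.** Suppose one covariate carries all of R² and is out of balance by 1.96 standard errors. The unadjusted comparison then shifts by 1.96·√R² standard errors: 0.62, 0.88 and 1.07 at R² of 0.10, 0.20 and 0.30. If the shift favors BPL HRIG, the error rate of a nominal 2.5% test, given that imbalance, is 1 − Φ[1.96(1 − √R²)/√(1 − R²)] = 7.9%, 11.3% and 14.5%. At R² of 0.02 it is 4.5%. Subgroup tables leave this shift in place; ANCOVA removes it.

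**The case against.** The strongest reply is that nothing here is invalid. A 1:1 randomized comparison without covariates keeps its error rate, because that rate already allows for chance imbalance. The figures in step 7 are conditional on a bad draw; averaged over randomizations, the unadjusted test is correct. The primary decision does not involve these models, and at 98% success adjustment would offer it little. All of this stands.

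A reader might infer that chance ANOVA p-values decide which subgroups are reported. The documents do not say so. SAP 8.b and 8.j are not linked, no baseline significance level is set, clinical relevance is a second ground for subgroups, and the main factors are already named. The 30% figure describes how often a test might flag something, not how subgroups are selected.

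The benefit may also be small. HRIG is dosed per kg at actual potency and weight is capped at 95.5 kg, so dosing already deals with some body-size variation. Pre-dose titer is of little use as a covariate, because subjects at or above the LLOQ are excluded. Neither document supports a floor on R², so the range has to start at zero.

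Finally, the models are not wholly closed: the SAP speaks of an appropriate mixed model and of standard model building for the GEE. But covariates chosen that way are not pre-specified, and the GEE covers only the proportions. Dividing by actual dose in the exploratory PK analysis is not covariate adjustment.

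**Conclusion.** The point holds as a low-cost improvement to secondary analyses, not as the repair of an error. The baseline test is uninformative, and unsuitable for race. Subgrouping is the only named response to imbalance and does not correct the overall estimate. The median rule cannot be applied to sex or race. The AUC0-7d t-test has no covariates and the GMT model names none.

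The size is uncertain because R² and CV are assumptions. The standard error falls by 0 to 16%. On the 0.80 bound, AUC0-7d power moves between R² = 0 and R² = 0.30 from about 94% to 99% at CV 40%, 81% to 93% at CV 50%, and 68% to 83% at CV 60%. At low R² the change is a point or two. If the 0.833 bound governs, the starting power at CV 50% is only about 65%.

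It would be wrong to conclude that the planned AUC0-7d or GMT comparisons are biased by design, or that the primary result or the 73 per group is in doubt.

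**What to change.** - **SAP 8.f, AUC0-7d:** replace the t-test with an ANCOVA of log AUC0-7d with treatment, age, sex and BMI, keeping the same margin and confidence-interval rule. First reconcile the two bounds (0.80 and 0.833) in that section.
- **SAP 8.f, GMTs:** name age, sex and BMI as fixed covariates in the mixed model for log titer. The unadjusted results can be kept as supportive.
- **SAP 8.b:** delete the ANOVA and describe the arms by summary statistics only.
- **SAP 8.j and protocol 10.8:** remove imbalance as a ground for subgroup analysis and list the subgroups in advance. Use categories for sex and race, and the median only for age and BMI.

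The cost is a few sentences and three covariates in two models. No new data and no change in sample size are needed. The change should be made before unblinding, since the value lies in pre-specification.
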